4.1.2 Exclusion Criteria

Subjects must not be enrolled into the study if they meet any of the following exclusion criteria:

1. Current diagnosis of type 1 diabetes mellitus.
2. Known medical history or clinical evidence suggesting non-diabetic renal disease, except for concomitant hypertensive nephrosclerosis or a single kidney.
3. History of acute kidney injury (AKI) within 1 year before Screening and change in SCr from Visit 1 to Visit 2 (Day -21) > 0.3 mg/dL (26.5 µmol/L) by central laboratory assessment.
4. History of chronic dialysis or renal transplant; active on a kidney transplant waiting list (awaiting transplant) with a living donor identified, or anticipated transplant within 6 months following randomization in the study.

5. Requirement for concomitant treatment with any prohibited concomitant medication, as indicated in [Section 7.3](#).
6. Uncontrolled hypertension defined as: SBP > 160 mmHg or DBP > 100 mmHg. See also Randomization Criteria ([Section 4.1.3](#)).
7. New York Heart Association heart failure Class III or IV within 1 year before Screening.
8. Myocardial infarction, unstable angina, revascularization procedure (eg, stent or bypass graft surgery), cerebrovascular accident, transient ischemic attack, or new clinically important electrocardiogram (ECG) findings within 6 months before Screening, or a revascularization procedure is planned during the study.
9. Left ventricular ejection fraction (LVEF) < 50% by echocardiogram (ECHO).
An ECHO performed for non-study-related reasons within 3 months before Screening can be used to satisfy this criterion.
10. Troponin-I levels > upper reference limit (URL). See also Randomization Criteria ([Section 4.1.3](#)).
11. B-type natriuretic peptide (BNP) > 200 pg/mL.
12. Alanine transaminase > 2x the ULN.
13. Subject is unable to tolerate SC test infusion.
14. Pregnant, breastfeeding, or not willing to cease breastfeeding.
15. History of cancer within 5 years before Screening, with the following exceptions:
 - Basal cell carcinoma of the skin
 - Squamous cell carcinoma of the skin
 - Carcinoma in-situ of the cervix
 - Carcinoma in-situ of the breast
 - Incidental histologic finding of prostate cancer (Stage T1a or T1b using TNM clinical staging)
16. Positive viral test result for hepatitis B virus (HBV) ([Appendix 2](#)), hepatitis C virus, or human immunodeficiency virus -1 / -2 at Screening.

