The incidence of potentially clinically significant abnormal values for selected laboratory measurements will be summarized by visit during the Treatment Period and Follow-up Period. [Table 3](#) gives the ranges of potential clinical concern for selected laboratory measurements.

The denominator in percentage calculation at a scheduled visit will be based on the number of subjects with a non-missing value at that particular visit.

Mean plots +/- SD over time will be provided for lab parameter of hematology and serum biochemistry. Hy's law plots for AST versus bilirubin (total) and ALT versus bilirubin (total) will be provided.

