**Table 3 Laboratory Values of Potential Clinical Importance**

Laboratory Parameter	Potential Clinical Importance Range	Unit
ACR (Urine)	Change from baseline $\geq 1.5$	mg/g
Platelet Count	<40 or >999	$10^3$ /UL
Hematocrit	<20 or >60	%
Hemoglobin	<7 or >20	g/dL
White Blood Cell Count (WBC)	<3 or >20	$10^9$ /L
Neutrophil Count	<1.5	$10^9$ /L
Serum Creatinine	Change from baseline (>0.3 and <0.7) OR Change from baseline $\geq 0.7$	mg/dL
Fasting Glucose	<70 or $\geq 250$	mg/dL
Nonfasting Glucose	<40 or >450	mg/dL
Potassium	<3 or $\geq 5.5$	mEq/L
Troponin-I	>ULN	ng/mL
Alkaline phosphatase	>2 x ULN	U/L
Total bilirubin	>2 x ULN	$\mu$ mol/L
ALT/SGPT	>3 x ULN	U/L
AST/SGOT	>3 x ULN	U/L

A by-subject listing of all laboratory values including flag for values out of normal range and clinical importance will be provided. Listings will include in general all visits (scheduled and unscheduled).

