## 11.4.2 Vital Signs

The vital signs will be summarized by visit and by the three randomized treatment groups and a combined CSL346 treatment group. The summaries will be provided for the analysis population as described in [Section 11](#).

The following summaries will be provided for systolic and diastolic blood pressure, heart rate, body temperature and body weight:

- Values of vital signs by scheduled visit,
- Change from baseline by scheduled visit.

Vital signs will be assessed as a triplicate measurement. For purpose of analysis the mean value of such triplicate parameter assessments will be used.

Vital sign values of potential clinical importance will be determined by using the criteria detailed in Table 4. The number and percentage of subjects with vital signs of potential clinical importance will be summarized by visit and at any time for the three randomized treatment groups and a combined CSL346 treatment group.

A by-subject listing of all vital sign data (scheduled and unscheduled visits) will also be presented. The listing will include a flag for values of potential clinical importance.

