## 11.4.3 ECG

The ECG parameter (PR interval, QRS duration, QT interval, QTcF, QTcB, heart rate) and their changes from baseline will be summarized by visit and by the three randomized treatment groups and a combined CSL346 treatment group. The summaries will be provided for the analysis population as described in [Section 11](#).

ECG assessments will be done as a triplicate measurement. For purpose of analysis the mean value of such triplicate parameter assessments will be used.

For QTcF, PR interval, QRS interval and heart rate, values of potential clinical importance will be determined by using the criteria detailed in Table 5. The number and percentage of subjects with those values of potential clinical importance will be summarized by visit and at any time for the three randomized treatment groups and a combined CSL346 treatment group. Subgroup summaries will also be provided by gender. The overall interpretation of ECG will be summarized at the same time points and treatment groups.

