**Table 5 ECG Parameters of Potential Clinical Importance**

ECG Parameter	Potential Clinical Importance (PCI) Range	Unit
QTcF Interval	>450 OR <500 or $\geq$ 500 OR $\geq$ 500 OR increase from Baseline $\geq$ 60 or increase from Baseline between >30 and <60	msec
Absolute PR Interval	<120 or >210	msec
Absolute QRS Interval	<75 or >110 or >120	msec
Heart rate	<50 or $\geq$ 120	bpm

A by-subject listing of all ECG data (scheduled and unscheduled visits) will also be presented. The listing will include a flag for values of potential clinical importance.

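### Most outlier limits in SAP Tables 3 to 5 carry no baseline condition, so the planned counts mix abnormalities present before dosing with new ones

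*SAP*

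**What the plan says.** **Laboratory (SAP 11.3, Table 3).** "The incidence of potentially clinically significant abnormal values for selected laboratory measurements will be summarized by visit during the Treatment Period and Follow-up Period". The denominator follows: "The denominator in percentage calculation at a scheduled visit will be based on the number of subjects with a non-missing value at that particular visit". Two of the 15 rows, ACR and serum creatinine, are defined by change from baseline. The other 13 are absolute.

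**Vital signs (SAP 11.4.2, Table 4).** "The number and percentage of subjects with vital signs of potential clinical importance will be summarized by visit and at any time". The hypertensive row combines absolute limits with a rise-from-baseline limb. The other three rows are absolute.

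**ECG (SAP 11.4.3, Table 5).** The wording is parallel: "subjects with those values of potential clinical importance will be summarized by visit and at" any time. QTcF combines absolute limits with increases from baseline. PR, QRS and heart rate are absolute; QRS, for example, is flagged at "<75 or >110 or >120" msec.

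**Related rules.**
- SAP 8.2.5 lets unscheduled values contribute to these counts and does not restrict them to values after dosing.
- SAP 8.4 starts the Treatment Period at randomization, not at first dose.
- Protocol 8.6.4.1.1 places the pre-dose Visit 4 blood samples and ECG after randomization.
- SAP 11.2 and Table 2 define treatment emergence for adverse events in detail. Outlier values have no counterpart.

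**The concern.** A table of incidence should count subjects who become abnormal. As written, a subject outside an absolute limit before the first infusion is counted at every later visit where the value persists, and again in the any-time count.

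Pre-existing abnormality is plausible in this population. Subjects have type 2 diabetes with HbA1c up to 12%, are on ACE inhibitor or ARB therapy unless intolerant, and may have eGFR down to just above 20 once the IDMC endorses it. Table 3 flags fasting glucose below 70 or at least 250 mg/dL and potassium of at least 5.5 mEq/L, and no numeric entry limit covers either. On the ECG side, exclusion criterion 8 covers only "new clinically important electrocardiogram (ECG) findings within 6 months before Screening". A long-standing conduction abnormality is therefore admissible and would be flagged throughout.

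At stake is how readable the between-arm outlier counts are, including ECG outliers that bear on the cardiac risk listed in Protocol Table 1.

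**Working it through.** **1. The plan's own figure.** The documents give no figure for these tables. The one design figure is reproduced only to confirm the group sizes. With 47 per group, difference 0.315, SD 0.65 and one-sided alpha 0.10, the standard error is 0.65 × √(2/47) = 0.134. Power is Φ(0.315/0.134 − 1.282) ≈ 0.857, against 85% stated. Nothing below affects it. Planned groups are 25 / 25 / 50 (SAP 4.4).

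**2. Row count.**

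| Table | Rows | Absolute only | Change from baseline only | Mixed |
|---|---|---|---|---|
| 3 Laboratory | 15 | 13 | 2 (ACR, creatinine) | 0 |
| 4 Vital signs | 4 | 3 | 0 | 1 (hypertensive AESI) |
| 5 ECG | 4 | 3 | 0 | 1 (QTcF) |
| Total | 23 | 19 (83%) | 2 | 2 |

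**3. Where entry criteria already remove the problem (Protocol 4.1.2 and 4.1.3).** ALT above 2x ULN is excluded, and the flag is above 3x. Troponin-I above the reference limit is excluded at Screening and at Visit 3. Randomization needs BP no higher than 150/100, and the absolute hypertension flags are 180/120. Glucose, potassium, PR, QRS, heart rate and absolute QTcF have no matching numeric limit.

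**4. Dilution.** Assumptions, none from the documents:
- a fraction b of every arm meets the limit at baseline and stays there;
- new onset among the rest is 5% on placebo and 20% on pooled CSL346, a true risk ratio of 4.0.

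The crude risk is b + (1 − b) × p. At b = 10%:
- placebo: 0.10 + 0.90 × 0.05 = 0.145;
- CSL346: 0.10 + 0.90 × 0.20 = 0.280;
- ratio: 0.280/0.145 = 1.93.

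The risk difference shrinks less, from 15 to 13.5 points, because it is multiplied only by (1 − b). Restricting to subjects not meeting the limit at baseline restores 4.0.

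**5. Chance imbalance at baseline.** With no drug effect, the probability that two arms differ by 10 points or more in b was found by exact enumeration of two independent binomials.

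| b | Crude risk ratio (true 4.0) | Crude difference (true 15 points) | Gap ≥ 10 points, 25 v 50 | Gap ≥ 10 points, 50 v 50 |
|---|---|---|---|---|
| 2% | 3.13 | 14.7 | 1.2% | 0.3% |
| 5% | 2.46 | 14.2 | 8.7% | 3.9% |
| 10% | 1.93 | 13.5 | 21.7% | 13.1% |
| 20% | 1.50 | 12.0 | 35.8% | 25.9% |
| 30% | 1.31 | 10.5 | 42.4% | 32.6% |

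**6. Pre-dose values.** The Treatment Period begins at randomization, and Protocol 8.6.4.1.1 puts the Visit 4 samples after it, so read literally a pre-dose sample falls inside the laboratory table. Protocol 8.6.4.1.2 lists randomization with the dosing procedures, so the order is not firmly fixed. Pre-dose values can be included, but the documents do not settle whether they will be.

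**The case against.** The strongest case is that the tables already protect the signals that matter most and that other output fills the gap.

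- **Renal, blood pressure and cardiac rows.** Creatinine and ACR are change-from-baseline rows. The BP and QTcF rows contain rises from baseline. Troponin and high BP are screened out at entry. This stands, and it limits the point to the rows named above.
- **Other summaries.** Change-from-baseline summaries are planned for laboratory, vital signs and ECG, with shift tables for hematology and chemistry and flagged listings. Protocol 9.1.1 spares sites from reporting as adverse events values already abnormal at screening unless they worsen. This stands in part. The shift tables use the normal range rather than the Table 3 limits and compare baseline with Week 24 or the last value. Week 24 is 12 weeks after the final dose, so a transient on-treatment outlier can be missed. Vital signs and ECG have no shift table, mean changes do not identify new outliers, and listings give no count by arm.
- **Assumed rates.** No document supports 10% or any other baseline rate, and glucose or potassium need not persist. This stands. At 2% or less, as is plausible for very low platelets or hemoglobin, the chance of a 10-point gap against a dose arm is at most 1.2%.
- **Missing pre-dose row.** A reader might infer that the laboratory table has no baseline row at all. The documents do not support that, since the Visit 4 row may itself be pre-dose. Table shells are also in a separate document (SAP 3).
- **Heart-rate limits.** Table 4 flags below 40 or above 110 bpm, and Table 5 flags below 50 or at least 120. A reader might call this a contradiction. The two tables cover different sources, vital signs and ECG, so a deliberate difference is possible but is not stated.

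**Conclusion.** The point holds for the 19 absolute-only rows and the absolute limb of QTcF. It matters mainly for glucose, potassium, PR, QRS, heart rate and absolute QTcF. For these, what is called incidence is by-visit prevalence, possibly with pre-dose values included.

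On the illustrative assumption of 10% persistent baseline abnormality, a true ratio of 4.0 appears as about 1.9, and a baseline gap of 10 points or more between a 25-subject dose arm and placebo arises by chance about 22% of the time. Both figures depend on assumed rates.

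Two stronger readings are tempting and unsupported. One is that Tables 3 to 5 ignore baseline throughout; four rows do use it. The other is that the comparison is biased. Randomization balances pre-existing abnormality in expectation, so the consequence is dilution or chance imbalance. No test is planned on these counts, so a loss of power would not describe any planned analysis. The tables are descriptive, and the primary analysis and sample size are untouched. This is a worthwhile, inexpensive improvement to safety reporting.

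**What to change.** In SAP 11.3, 11.4.2 and 11.4.3, for absolute limits:

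1. Count a subject as treatment-emergent if a value after first IP meets the limit and the baseline value (SAP 8.2.3) does not.
2. Use as denominator the subjects who do not meet the limit at baseline and have a post-baseline value.
3. Show subjects meeting the limit at baseline in a separate row by arm.
4. Define the any-time count as after first IP, including unscheduled values.
5. Leave the change-from-baseline limits in their present form.

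Before applying this, settle two entries. The QTcF row in Table 5 joins above 450 and below 500 msec with OR, which read literally flags every value. The heart-rate limits of Tables 4 and 5 should be reconciled, or the SAP should state that they differ on purpose by source.

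The cost is a few sentences and one condition in the table programs, with no new data. The downside is that worsening in subjects already abnormal at baseline appears only in the separate row and the listings. The denominators also shrink slightly: at 10% baseline abnormality, an expected 25 × 0.90 = 22.5 subjects per dose arm.

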**Table 3 Laboratory Values of Potential Clinical Importance**

Laboratory Parameter	Potential Clinical Importance Range	Unit
ACR (Urine)	Change from baseline $\geq 1.5$	mg/g
Platelet Count	<40 or >999	$10^3$ /UL
Hematocrit	<20 or >60	%
Hemoglobin	<7 or >20	g/dL
White Blood Cell Count (WBC)	<3 or >20	$10^9$ /L
Neutrophil Count	<1.5	$10^9$ /L
Serum Creatinine	Change from baseline (>0.3 and <0.7) OR Change from baseline $\geq 0.7$	mg/dL
Fasting Glucose	<70 or $\geq 250$	mg/dL
Nonfasting Glucose	<40 or >450	mg/dL
Potassium	<3 or $\geq 5.5$	mEq/L
Troponin-I	>ULN	ng/mL
Alkaline phosphatase	>2 x ULN	U/L
Total bilirubin	>2 x ULN	$\mu$ mol/L
ALT/SGPT	>3 x ULN	U/L
AST/SGOT	>3 x ULN	U/L

A by-subject listing of all laboratory values including flag for values out of normal range and clinical importance will be provided. Listings will include in general all visits (scheduled and unscheduled).

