### 8.2.4 Change from Baseline

Change from baseline is calculated as:

- visit value – baseline value.

Percentage change from baseline is calculated as:

- (change from baseline / baseline value) \* 100.

Percent change for geometric mean ACR is calculated as:

- ((geometric mean ACR at a visit / baseline geometric mean ACR) – 1) \* 100%.

If either the baseline or visit value is missing, the change from baseline and percentage change from baseline is missing.

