### **10.1 Analysis of Primary Endpoint(s)**

#### **10.1.1 Primary Estimand**

The primary interest is to quantify the treatment effect of CSL346 under the situation where SGLT2i may be a possible effect modifier and is included in the model. The estimand for the ITT Analysis Set is the average effect of CSL346 on the geometric mean ACR at 16 weeks averaged across subjects receiving and not receiving SGLT2i. All data collected through Week 24 will be used in the analysis.

The primary estimand in line with the primary interest of the study is described as follows:

- Treatment Condition: four SC administrations of CSL346 or placebo over a 12-week period (Day 1, Weeks 4, 8 and 12) where the primary comparison is between CSL346 at Week 16, regardless of dose, and placebo, while subjects have not died. The “treatment policy strategy” will be used, i.e. changes in dose, for example from 16 mg/kg to 8 mg/kg OR the number of subcutaneous injections, or treatment discontinuation/non-initiation, or other miscellaneous factors influencing ACR will not be taken into account in the primary analysis;
- Population: the target patient population defined by T2DM and DKD and further eligibility criteria;

- Variable: change from baseline at 16 weeks of log ACR;
- Population-level summary: difference in treatments, calculated as  $100\% \times (\text{geometric mean ratio of the treatment comparison} - 1)$  based on log ACR.

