## 16 Appendices

### 16.1 SAS Code

SAS code for MMRM analysis

```
Ods graphics on;
Proc mixed data=data_set method=reml plots=residualpanel;
  Class treatment visit patient sglti_yn;
  Model chglnacr =treatment visit baseline sglti_yn
  treatment*visit sglti_yn*visit baseline*visit / alpha=0.20 cl
  ddfm=kr covb solution;
  Repeated visit / type=un subject=patient r rcorr;

* *** Estimate for treatment difference at 2 weeks *** *;
  Estimate "CSL08 vs. PBO at 2 weeks" treatment 1 0 -1
  treatment*visit 1 0 0 0 0 0      0 0 0 0 0 0      -1 0 0 0 0 0 / CL
  alpha=0.2;
  ESTIMATE "CSL16 vs. PBO at 2 weeks" treatment 0 1 -1
  treatment*visit 0 0 0 0 0 0      1 0 0 0 0 0      -1 0 0 0 0 0 / CL
  alpha=0.2;
  ESTIMATE "CSL vs. PBO at 2 weeks" treatment 0.5 0.5 -1
  treatment*visit 0.5 0 0 0 0 0      0.5 0 0 0 0 0      -1 0 0 0 0 0 / CL
  alpha=0.2;

* *** Estimate for treatment difference at 16 weeks *** *;
  Estimate "CSL08 vs. PBO at 16 weeks" treatment 1 0 -1
  treatment*visit 0 0 0 0 1 0      0 0 0 0 0 0      0 0 0 0 -1 0 / CL
  alpha=0.2;
  ESTIMATE "CSL16 vs. PBO at 16 weeks" treatment 0 1 -1
  treatment*visit 0 0 0 0 0 0      0 0 0 0 1 0      0 0 0 0 -1 0 / CL
  alpha=0.2;
  ESTIMATE "CSL vs. PBO at 16 weeks" treatment 0.5 0.5 -1
  treatment*visit 0 0 0 0 0.5 0      0 0 0 0 0.5 0      0 0 0 0 -1 0 / CL
  alpha=0.2;

  Lsmmeans treatment treatment*visit / diff cl;
run;
Ods graphics off;
```

Where:

- chglnacr is the repeated measure of change in log ACR collected at Weeks 2, 4, 8, 12, 16 and 24;
- treatment takes on three levels (CSL346 8 mg/kg, CSL346 16 mg/kg and placebo)

- sglt2i\_yn is the stratification variable associated with the presence or absence of a concomitant SGLT2i at entry into the trial;
- baseline is the baseline log ACR used as a covariate in the model;
- visit is the time variable;

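### SAP Table 3 flags urine ACR on an absolute rise of 1.5 mg/g, a criterion that about half of subjects with no true change would meet at any visit

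*SAP*

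**What the plan says.** The ACR row of SAP Table 3 reads "Change from baseline $\geq 1.5", with mg/g as the unit. SAP 8.2.4 gives the general definition of change from baseline as "visit value – baseline value". The same section defines percent change separately, and for ACR builds it on the ratio "geometric mean ACR at a visit / baseline geometric mean ACR". SAP Appendix 16.10 confirms mg/g as the reporting unit for ACR.

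The row has two uses. One is a count in SAP 11.3: "abnormal values for selected laboratory measurements will be summarized by visit". The other is the listing described below Table 3: "A by-subject listing of all laboratory values including flag for values out of normal range and clinical importance will be provided".

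Elsewhere the documents treat ACR change as relative. The estimand in SAP 10.1.1 has "Variable: change from baseline at 16 weeks of log ACR", and in SAP 16.1 "chglnacr is the repeated measure of change in log ACR". The two other ACR safety criteria are also ratios. Protocol 9.1.3.3 has a central-laboratory flag at 2 times baseline or more. SAP 11.2 defines the albuminuria AESI as a confirmed rise of more than 2-fold with further evidence of acute kidney injury.

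**The concern.** Entry requires an ACR of at least 150 mg/g, so a rise of 1.5 mg/g is a very small relative change in this population. Protocol 9.1.3.3 puts the within-subject CV of FMV ACR at about 30% and warns that random variation is hard to tell from an adverse effect. A threshold near 1% of baseline cannot make that distinction.

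At stake is how the safety output reads. Renal harm is a named potential risk (Protocol 1.4, Table 1), and evaluating albuminuria is part of its mitigation. If close to half of unchanged subjects are counted at each visit in every arm, the table says little about important rises, and the listing flag does not direct a reader to them.

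**Working it through.** **The plan's own figure.** SAP 4.4 and Protocol 10.1 assume an SD of 0.65 for the Week 16 change in ln ACR, a difference of 0.315 and one-sided alpha 0.10, and state 85% power with 94 subjects. The normal formula gives 2 × (1.2816 + 1.0364)² × 0.65² / 0.315² = 45.8, so 46 per arm or 92 in total. At 47 per arm the power is 85.7% (85.5% with the t distribution). The SD of 0.65 is therefore the figure the plan used.

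**Inputs for the flag.**
- Threshold: 1.5 mg/g, as a difference (SAP Table 3, SAP 8.2.4).
- Baseline: geometric mean of 6 FMVs. Visits: 3 FMVs, or 2 at Visit 9 (SAP 8.2.7).
- Within-subject CV: about 30% (Protocol 9.1.3.3).
- Illustrative baseline: 150 mg/g, the entry minimum (Protocol 4.1.1).

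**Noise SD on the ln scale**, assuming independent lognormal noise from day to day:
- One FMV: √ln(1 + 0.30²) = 0.2936.
- Change at a 3-FMV visit: 0.2936 × √(1/3 + 1/6) = 0.2076.
- Change at Visit 9: 0.2936 × √(1/2 + 1/6) = 0.2397.

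**Flag rate as printed.** P(flag) = 1 − Φ[(ln(1 + 1.5/baseline) − ln(true ratio)) / SD]. At baseline 150 mg/g, 1.5/150 = 1.0% and ln(1.01) = 0.00995.

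| Case | Noise only, 3 FMVs | SD 0.65 |
|---|---|---|
| No change, baseline 75 mg/g | 46.2% | 48.8% |
| No change, baseline 150 mg/g | 48.1% | 49.4% |
| No change, baseline 500 mg/g | 49.4% | 49.8% |
| True doubling, baseline 150 mg/g | over 99% | 85% |

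At Visit 9 the noise-only rate at baseline 150 mg/g is 48.3%. Specificity per visit at that baseline is thus about 51% to 52%. Sensitivity is not the problem.

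**Comparison with a ratio reading.** If 1.5 meant 1.5-fold, then with noise only:
- No change: 1 − Φ(0.4055/0.2076) = 1 − Φ(1.953) = 2.5%.
- True doubling: 1 − Φ((0.4055 − 0.6931)/0.2076) = Φ(1.386) = 92%.

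These two figures depend on independence between days. If the FMVs within a visit were perfectly correlated, the SD would be 0.2936 × √(1 + 1/2) = 0.3595. The rates would then be 13% and Φ(0.800) = 79%, while the rule as printed would flag 48.9% with no change. A ratio criterion separates change from noise in either case, and the printed one does not.

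**The case against.** The best defence is that the row is complete and its effect is small. It prints a number and a unit, SAP 8.2.4 says how to compute the change, and the serum creatinine row of the same table uses the same form with absolute mg/dL limits. Albuminuria safety does not rest on this flag: Protocol 9.1.3.3 has its own laboratory flag, confirmation sequence and IDMC review, and the AESI tables use investigator-marked events. The table shells are a separate document and may add detail. All of this stands. It limits the consequence but does not make 1.5 mg/g a workable threshold.

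A reader might infer more than the documents support:
- **That no scale is stated.** One is: an absolute difference in mg/g. It is implausible and unexplained, and that another was intended is an inference. Reading 1.5 as +150% or as natural-log units conflicts with the printed unit and has no support in Table 3.
- **That the flag has almost no specificity.** Per visit it is about 50%. It would fall further if flags were accumulated over visits, but SAP 11.3 plans the laboratory incidence by visit only. Contrast the ECG section: "The number and percentage of subjects with those values of potential clinical importance will be summarized by visit and at any time".
- **That rates at SD 0.65 are pure error rates.** That SD is a planning figure for the spread of Week 16 change across subjects and includes real individual change. For the printed rule this hardly matters (48% against 49%). For the 1.5-fold reading it matters a great deal: SD 0.65 gives 27% with no average change and 67% with a doubling, against 2.5% and 92% from noise.
- **That the QTcF cell of Table 5 is a second error of the same kind.** Its limits may be separate reporting bands run together when the text was read from the PDF, so it cannot be called a fault in the plan.

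**Conclusion.** The ACR criterion in SAP Table 3 is wrong as written, and the point is minor. Followed exactly, it flags about 48% of subjects per visit from measurement noise alone at a baseline of 150 mg/g, and 49% at SD 0.65.

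The result rests on lognormal noise, independence between days and no true change. It moves little when these inputs vary: 46% to 49% at an FMV baseline of 75 mg/g, and closer to 50% at higher baselines. Using SD 0.65 at visits other than Week 16 is an assumption. The 1% comparison is approximate, because entry uses a 24-hour collection and baseline uses FMVs; at an FMV baseline of 75 mg/g the threshold is 2%.

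That the ratio scale is the natural one follows from the documents' other two ACR safety criteria. Which cut-off was intended cannot be settled from the documents. Confidence is high on the printed rule and its flag rate, and lower on what was meant.

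**What to change.** Before database lock, correct the ACR criterion and unit in SAP Table 3. Express the flag as the ratio of the visit to the baseline geometric mean ACR, with no unit, and have the sponsor confirm the intended cut-off. Reconcile the row with Protocol 9.1.3.3 and the AESI definition in SAP 11.2, which themselves differ at the boundary (2-fold or more against more than 2-fold). Check that the table shells carry the same rule.

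The cost is one table row and the matching flag programming. Data collection and the primary analysis do not change.
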